1. PURPOSE OF STUDY

Every year in the United States alone, approximately 795,000 people will experience a new or recurrent stroke, with the vast majority of these being an acute ischemic stroke (AIS)¹. For every minute that a stroke goes untreated, 1.9 million neurons die, underscoring the importance of early identification and treatment². Additionally, it is estimated that half of all stroke patients enter the healthcare system via Emergency Medical Services (EMS)³. As such, evaluating potential interventions in the prehospital and emergency department (ED) phases of care is a key, yet often ignored, component of stroke treatment. Administration of 15L/min oxygen via a partial non-rebreather facemask to create systemic hyperoxia is a relatively low cost, potentially beneficial part of stroke care that could be implemented early in the prehospital and ED phases of care. However, this therapy has had conflicting results, with little data evaluating its potential benefits early after stroke onset, in the ED and prehospital phases of care, where most preclinical data suggests a potential benefit. *The central hypothesis of this study is that hyperoxia during the acute ischemic period of a stroke prior to potential recanalization decreases infarct volume and improves patient outcomes.* This clinical trial will evaluate the potential therapeutic role of hyperoxia when applied in the immediate ischemic period following a stroke in the controlled ED setting and will evaluate the effects of hyperoxia in stroke patients on the production of markers of free radical damage and inflammatory markers associated with hyperoxic lung injury.

2. BACKGROUND AND RATIONALE

Hyperoxia in stroke – therapeutic mechanism and biomarkers: Ischemic strokes are characterized by an infarct core comprised of cells having suffered irreversible damage in the setting of hypoxia that will progress to complete necrosis. This is surrounded by a “penumbra” of brain tissue, which is not yet irreversibly destined for cell death⁴. This penumbral zone contains cells whose metabolic and structural integrity have been compromised, but the damage is not irreversible should the cells be provided sufficient oxygen and metabolic substrates in a timely fashion. After the initial ischemic event, the penumbral tissue immediately surrounding the infarct core undergoes depolarization and subsequently increases its metabolic rate. Coupled with compromised cerebral blood flow and low oxygen supply, this creates a hypoxic environment that perpetuates tissue destruction and infarct size^{5,6}. Tissue damage resulting from this hypoxia is mediated in part by a shift to anaerobic metabolism which in turn leads to production of excess amounts of oxygen and nitrogen free radicals and ultimately lipid peroxidation, protein denaturation, DNA damage and activation of apoptotic pathways resulting in cell death^{7,8}.

The utility of biomarkers to lend insight into the molecular pathophysiology of stroke and to act as potential biomarkers of diagnosis, hemorrhagic conversion, and ultimately stroke severity remains an area of active research. In stroke, it is difficult to directly measure the production of reactive oxygen species (ROS) given their short half-life within brain tissue itself, let alone in peripheral serum. Previous groups have shown that increased production of downstream products of free radical-induced lipid peroxidation leads to neurologic deterioration⁹. MMP-9 is one matrix metalloproteinase that is activated downstream of these oxidative stress pathways and contributes to destruction of the blood brain barrier and increased cerebral edema after stroke. MMP-9 also correlates with infarct volume, clinical stroke severity, and hemorrhagic transformation after thrombolysis^{10,11}. IL-6 is an inflammatory cytokine that is increased during and after AIS in both astrocytes and microglia

and in peripheral leukocytes. Increased peripheral concentration of IL-6 in stroke correlates with stroke severity and the development of post-infarction infections^{12,13}. One potential mechanism of hyperoxia therapy based on data in rodent models suggests that the provision of increased levels of PaO_2 will raise the amount of oxygen available to the ischemic tissues and prevent further progression down this pathway toward cell death (Figure 1).

[figure not shown]

Figure 1: Proposed mechanism of hypoxic injury in AIS (A) and the mitigation of these effects with hyperoxia (B).

Hyperoxia in preclinical models: In rodent models of middle cerebral artery occlusion (MCAO), hyperoxia supplied shortly after the initiation of ischemia results in return of penumbral brain tissue oxygenation levels to near pre-ischemic levels and increases cerebral blood flow to ischemic tissues¹⁴⁻¹⁹. Furthermore, there is no increase in production of markers of ROS. In other rodent models, hyperoxia even blunted the production of matrix metalloproteinase-9 (MMP-9) and subsequently increased levels of two tight junction proteins involved in maintaining the blood brain barrier^{20,21}. Rodent models also correlated this decrease in ROS with decreases in markers of cell apoptosis^{14,22}. However, in gerbil brain ischemia models, hyperoxia was shown to increase ROS and lipid peroxidation²³. This potential mechanism for adverse effects of hyperoxia has not been evaluated in humans. We will examine the effects of hyperoxia in AIS on these biomarkers (IL-6 and MMP-9) and others.

While the above beneficial effects of hyperoxia were observed in rodents using a transient MCAO model to carefully control for the potential negative effects of oxygen during reperfusion, using a permanent middle cerebral artery occlusion (pMCAO) model also saw beneficial effects of hyperoxia²⁴. This model even showed an increase in systemic vascular resistance similar to prior observations in humans. However, despite the increase in systemic vascular resistance, hyperoxia still showed improved outcomes compared to controls and did not show a significant difference in cerebral blood flow to the contralateral hemisphere.

Furthermore, the window in which hyperoxia is supplied is a key determinant of the potential therapeutic benefit. Mice treated with hyperoxia during the acute ischemic phase of MCAO showed improved outcomes including increased partial pressure of oxygen in the penumbral tissue, improved function on neurobehavioral testing, and lower levels of necrosis^{25,26}. Importantly, these benefits were lost when hyperoxia was extended into the period of reperfusion where hyperoxia was associated with increased ischemic tissue damage and cerebral edema²⁷.

Hyperoxia in humans: A pilot study in which patients were treated with 45L/min humidified oxygen via facemask started within 12 hours of their last known well (LKW) and continued for 8 hours demonstrated reduced markers of anaerobic metabolism and increased markers of neuronal integrity and mitochondrial function in the hyperoxia treated group²⁸. Hyperoxia was also associated with an initial improvement in neurological function (measured by the NIHSS) and a significant difference in penumbral salvage at 4 hours (~70% in controls vs 120% in hyperoxia)²⁹. However, the difference did not meet significance at 24 hours. When hyperoxia was applied for even longer periods of time there was also no significant neurological improvement³⁰. Thus, like in the preclinical models, the duration of the hyperoxia may influence outcomes. Additionally, the dose of “hyperoxia” likely affects the potential therapeutic benefit. In patients treated with “hyperoxia” in the form of 3L nasal

cannula for the first 24 hours after admission, there was no difference in neurological outcomes^{31,32}.

As a group, these human studies were relatively small studies with an overall positive effect of hyperoxia when given at high levels and started relatively early after AIS onset. However, when initiated at lower supplemental oxygen levels and/or treated further from the onset of ischemia, there was no significant improvement in patient outcomes nor evidence of harm. Hyperoxia therapy is most likely to benefit patients in the early stages after initial ischemia by limiting progression to final infarct volume while awaiting spontaneous recanalization. This is supported by the most promising studies which used 45L/min oxygen therapy for 8 hours in patients presenting within 12 hours from LKW. Thus, we have designed our study to focus on early administration, prior to potential reperfusion, of high levels of supplemental oxygen, targeting a PaO₂ of 200-400mmHg as in the rodent models.

Hyperoxia in other diseases – safety concerns: The role of hyperoxia in stroke remains surrounded by controversy based on data from other disease states. Initial studies on the role of hyperoxia in myocardial infarction (MI) showed a reduction in the degree of myocardial necrosis³³⁻³⁵. However, further studies demonstrated potential harm through decreases in coronary blood flow, myocardial oxygen consumption and cardiac output, as well as through increases in systemic vascular resistance and myocardial reperfusion injury³⁶⁻³⁹.

Looking at a broader population of cardiac patients, a meta-analysis of patients with PaO₂ ranging from 234-604mmHg who presented with heart failure, coronary artery disease (CAD), recent coronary artery bypass grafting (CABG) surgery, or sepsis found that compared to controls, hyperoxia overall resulted in decreased heart rate, decreased cardiac output and increased systemic vascular resistance⁴⁰. However, these changes were not consistent amongst all disease entities. CAD and post-CABG patients showed decreased heart rates, but this was not seen in heart failure or in sepsis patients. Cardiac output was decreased in CAD and heart failure patients but not in post-CABG nor in septic patients. Thus, while there continue to be concerns regarding potential harmful hemodynamic and cardiovascular effects of hyperoxia, these risks appear somewhat disease-state specific. At best, in states with a baseline impaired cardiac function, hyperoxia has no overall benefit, with the possibility for negative hemodynamic consequences.

Hyperoxia is associated with cerebral vasoconstriction in healthy subjects. Thus, it is also important to evaluate hyperoxia in the context of other brain injury states in which this potential vasoconstriction could be detrimental, such as traumatic brain injury (TBI). In TBI, hyperoxia provided in the first 48 hours increases the partial pressure of oxygen in brain tissue and reduces brain tissue lactate levels, corresponding to an improved prognosis⁴¹. In a clinical trial of severe TBI patients, hyperoxia resulted in: 1) improved cerebral metabolic rates of oxygen, 2) decreased lactate levels, 3) increased brain tissue oxygen levels, and 4) no increase in markers of hyperoxic lung injury (as measured by surrogate lung inflammatory biomarkers, IL-6 and IL-8)⁴². Despite these findings, safety concerns stemming largely from the potential for acute oxygen toxicity leading to the accumulation of ROS and free radicals leading to lung injury and lipid peroxidation of brain tissue limit the use of hyperoxia in TBI. While this remains the leading argument for not using hyperoxia, a recently published pilot study examining the use of hyperoxia in severe TBI, again showed no difference in the production of ROS⁴³.

The most commonly proposed mechanism of potential harm from hyperoxia therapy is the increased production of ROS that could not only contribute to reperfusion injury, but might also lead to hyperoxic lung injury. This issue has also been evaluated in rodent and human models of critically ill patients, through induced endotoxemia. Here, brief hyperoxia with a PaO₂ of ~400mmHg for 3.5 hours in humans resulted in no change in the ability to

mount a cytokine and inflammatory response⁴⁴. Both hyperoxic and control subjects had similar patterns of expression of tumor necrosis factor alpha (TNF- α), interleukin-6 (IL-6), IL-8, or IL-10 in response to endotoxemia. Additionally, hyperoxia treatment did not clinically alter the leukocyte population produced in response to endotoxemia. Hyperoxic lung injury has been demonstrated in patients exposed to hyperoxia for long periods of time but has not been evaluated in those with brief hyperoxia exposures^{45,46}. Furthermore, rodent MCAO models suggest that this risk is low in stroke given there was no evidence of such effects when therapy was instituted immediately after the ischemic event¹⁴⁻¹⁹. Thus, by limiting the oxygen therapy in this clinical trial to no more than 4 hours, the study will minimize this potential risk.

Potential risks of hyperoxia in stroke: Further safety concerns regarding possible increased mortality resulting from hyperoxia therapy were raised in a multicenter retrospective study that determined the 28-day mortality in mechanically ventilated intensive care unit (ICU) stroke patients (including ischemic stroke, subarachnoid hemorrhage (SAH), and intracerebral hemorrhage (ICH)). This study found an increased mortality in stroke patients found to be hyperoxic at 24 hours after admission⁴⁷. These patients were exposed to longer durations of hyperoxia than proposed in this current study. Additionally, upon subgroup analysis, increased mortality was only seen in the hyperoxic SAH and ICH groups compared to normoxic controls, and there was no significant difference in mortality in the AIS patients exposed to hyperoxia⁴⁷. This was further supported by a second study of ICU stroke patients being mechanically ventilated that failed to demonstrate an association between oxygenation level (PaO_2) and mortality⁴⁸. The safety of hyperoxia in AIS patients was also questioned in a recent unpublished clinical trial (NCT00414726) studying hyperoxia, that randomized patients to room air or 45L/min via facemask. The trial was terminated early, after enrolling only 85 participants, for safety concerns⁴⁹. However, upon closer blinded review of the results, only one death in each group was determined to be possibly related to the therapy. The remainder (16/43 deaths in the hyperoxia group, 6/41 deaths in normoxia group) were determined to be unrelated to therapy. Taken together, these data suggest that the safety of hyperoxia therapy is disease-specific and short exposures to hyperoxia prior to recanalization in AIS patients are safe. However, the beneficial immediate and long-term effects of brief hyperoxia in AIS are not fully understood.

The results of the proposed study have important implications for the acute treatment of stroke. Oxygen therapy is a simple, low cost treatment that could be instituted at the point of first contact with the healthcare system for many patients, in the prehospital and ED phases of stroke care. While the European PROOF trial of hyperoxia for acute stroke recently began enrollment, it randomizes patients to receive 40L/min supplemental oxygen, a level that is not currently feasible in the prehospital setting and that lacks data to suggest it is necessary for a beneficial effect. Additionally, this therapy is to begin within four hours of subject's non-contrast CT-head and extends further into the period of potential reperfusion. Thus, understanding the effects of hyperoxia provided at more feasible and tolerable levels and proximate to the onset of symptoms has the potential to impact many patients who are otherwise lacking potential therapeutic options, some of whom are already being exposed to oxygen therapy in the prehospital setting. The proposed project will inform the design of a future clinical trial of hyperoxia and will provide the needed experience and preliminary data to develop a career in clinical emergency medicine research emphasizing the treatment of acute stroke.

3. ADMINISTRATIVE ORGANIZATION

This study will be conducted at the University of Colorado Hospital (UCH) Anschutz Medical

Campus and the UCH-Memorial Central Hospital. Subjects will be recruited, enrolled, and therapy initiated upon presentation to the Emergency Department. Arterial Blood Gas (ABG) samples will be drawn and immediately processed per their standard protocol for routine ABG testing. Venous serum samples will also be collected and processed for storage in the Emergency Medicine Research Lab or the clinical labs of the UCH-Memorial and subsequently transferred to their research storage. All serum biomarker analyses will occur in aggregate at the end of subject recruitment.

4. STUDY DESIGN

This is a multicenter, prospective, randomized, controlled, feasibility study to evaluate the feasibility of early brief hyperoxia therapy for AIS in the ED and to gather preliminary data on the potential therapeutic and adverse effects of such intervention. It is hypothesized that global hyperoxia treatment in the acute ischemic period of a stroke prior to potential recanalization will decrease infarct volumes and improve neurologic outcomes in AIS patients without increasing the production of markers correlating with ischemic-reperfusion injury and the hyperoxic lung injury. To test this hypothesis, subjects will be randomized equally between the placebo (medical air) and hyperoxia (supplemental oxygen) treatment groups.

[figure not shown]
For the purpose of this study, we define normoxia as a pulse oximetry of 94% or greater, although per AHA guidelines, supplemental oxygen is recommended only in patients with a pulse oximetry of less than 94%⁵⁰. Based on rodent models that targeted systemic hyperoxia with a PaO₂ of 200-400mmHg, hyperoxia will be defined as a PaO₂ of >200mmHg. Previous literature demonstrated that 10-15L/min facemask resulted in the PaO₂ of 425 +/- 43mmHg in patients undergoing cardiac catheterization found to have clean coronary arteries and 403 +/- 49mmHg in those with CAD⁵¹. Thus, treatment with 15L/min should be sufficient to achieve this level of hyperoxia in this study population, and will be confirmed through ABG sampling at 4 hours after initiation of treatment intervention.

Patients who are found to require supplemental oxygen according to AHA guidelines will be provided such intervention with careful documentation of the timing, duration, and dose of supplemental oxygen provided.

The design will proceed as follows: (see Figure 2)

- Randomize subjects between placebo and supplemental oxygen via partial non-rebreather facemask at 15 L/min.
- Collect study measurements
- Perform 3-month follow up for mRS
- The study duration is estimated at 30 months to allow sufficient time for subjects enrollment and completion of their 3 month follow-up

In order to minimize bias, efforts will be made to blind the observers to the control versus treatment group. However, medical air and oxygen have different ED wall supply connectors that could be potentially identified by both the patient and the study personnel. Thus, full blinding cannot be guaranteed. To minimize bias, ED staff will initiate a given intervention and they will be instructed to not tell the patient which was started on the patient. To avoid bias with regards to infarct lesion size,

the automated RAPID software will be used to perform lesion measurements and screening for enrollment based on target mismatch. The CT-Perfusion and automated CT-ASPECT (Alberta Stroke Program Early Computed Tomography Score) have been previously used to identify patients who are early in their acute stroke trajectory with a small core infarct volume and remaining area suggestive of salvageable tissue⁵². Both are standardized quantitative or semi-quantitative measurements that can be automatically computed by RAPID software, thereby eliminating the subject assessments of providers to identify patients with potentially salvageable penumbral tissue. The assessment of the NIHSS will be extracted from the initial stroke team consult note and subsequent assessments will be video-recorded by study personnel. Videos of the assessment will be stored using a unique file name and stored in the secure School of Medicine Server. They will be reviewed in groups in a blinded fashion for scoring. At the conclusion of the study and required time for maintaining study data, all videos will be destroyed. In the case where videotaping is not permitted by a performance site, NIHSS-trained personnel (RN, MD, or PA) who are caring for the patient, will be asked to complete and score the NIHSS. In the event that the clinical team is unable to complete this assessment, the research team, also NIHSS-trained, will complete this assessment. In all cases, who/how the NIHSS was completed will be documented and blinding to the study intervention will be attempted when possible.

The primary study outcome is to determine the feasibility of enrolling and randomizing AIS patients to a therapeutic intervention within less than one hour of ED presentation. Secondary outcomes of potential therapeutic effect to inform future clinical trial(s) include penumbral salvage at repeat imaging, change in NIHSS over the first 24 hours, and 3-month mRS. To assess potential adverse effects on markers of worsening stroke severity and possible hyperoxic lung injury, levels of MMP-9, IL-6, and IL-8 will be measured at initiation, 4 hours and 24 hours. Further analysis of additional biomarkers will be considered in the future.

4.1. SUBJECT POPULATION

Eligible subjects will include acute ischemic stroke (AIS) patients aged 18 years or older who present to the UCH ED. There will be no specific selection of subjects based on sex, race or ethnicity, age, or socioeconomic status. We anticipate the study population to be representative of that of the greater Colorado Springs and Aurora, CO area with the exception that stroke prevalence increases with age and this will likely be reflected in the final study population.

Subjects with a suspected stroke who are normoxic at baseline (room air SpO₂≥94%) and have either 1) a target mismatch lesion on CT-perfusion [defined by RAPID automated software demonstrating a ratio of PWI_{Tmax>6} lesion volume/Infarct volume (with cerebral blood flow <30% normal) greater than 1.2 or 2) a non-contrast CT-head RAPID ASPECT score of 10 (suggesting a patient has not completed their infarct), a NIHSS≥ 1, and a LKW ≤ 12 hours will be screened for eligibility. While some vulnerable populations (i.e. children and prisoners) will be excluded, AIS by the nature of the disease has the potential to impair a subject's capability to give informed consent and places them in the category of a vulnerable population. All subjects will be evaluated for the ability to give informed consent through use of the University of California, San Diego, Brief Assessment of Capacity to Consent (UABCC) Form⁵³. In cases where the subject is determined to lack the ability to provide consent, the subject's legally authorized representative (LAR) will be approached. Consent forms describing in appropriate detail the study interventions, study procedures, and risks will

be given to the participant and/or their LAR. If and when the study subject regains capacity, they will be approached for continued participation. If the subject/LAR consents for participation he/she will sign the informed consent form prior to any study procedures being done.

In terms of potential pregnant women, it is anticipated that most women will be older than likely childbearing age. While supplemental oxygen use in pregnant women experiencing fetal distress is routine, the effects of maternal hyperoxia on a developing fetus are unknown. Those of likely childbearing potential will be excluded. If a subject withdraws for any reason from the study, he/she will be replaced to meet the enrollment goal when possible. Our target enrollment will be 200 patients (~100 per arm).

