7. STUDY PROCEDURES

As part of the screening and enrollment process, patients with suspected AIS will have either a non-contrast CT head with RAPID calculation of ASPECT score or a CT-perfusion head. Using standard stroke alert treatment protocols at this institution, the RAPID software is used in most potential stroke patients at our institution and will be used to calculate infarct and penumbral volume and targeted diffusion/perfusion mismatch for this study. As part of the screening process, medical charts and EMS reports will be accessed by study personnel as needed to ensure potential subjects meet all inclusion/exclusion criteria. The screening and enrollment procedures along with collection of initial vitals will occur almost simultaneously given the very acute nature of the presentation and desired short interval from ED presentation to randomization. No data will be collected during the screening process that is not part of routine patient care prior to subject enrollment. Routine patient demographics, past medical history, medications, and prehospital assessments will be obtained from chart review. No research data that is not already part of routine patient care will be entered into the subject medical records. Randomization will occur in a 1:1 fashion between the two treatment groups. The estimated study duration is 30 months to allow for full enrollment of subjects and the 3-month mRS assessment. Each subject will be followed for a total of 90 days from enrollment to final assessment. No results from this study will be shared with subjects.

[figure not shown]
Once consented and enrolled in the study, subjects will have the following procedures: (See Table 1 for Schedule of Activities).

1. *Infarct progression:*

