- a. Initial CT-perfusion head or non-contrast CT-Head with RAPID ASPECT score – multimodal CT-head imaging will be obtained upon ED presentation according to local stroke protocols. Targeted mismatch criteria will be based on previous standards identified in the DEFUSE 3 trial, using RAPID generated CT maps (RAPID, iSchema View, Menlo Park, CA)⁵⁷. This study measurement will be completed as part of the screening process to ensure eligibility with regards to a target mismatch lesion. However, upon completion of the CT-perfusion or non-contrast CT-Head, the total volume of at-risk tissue (both penumbral and infarcted tissue) will also be determined and recorded. This is part of the routine medical treatment for acute stroke patients.
- b. Follow-up MRI-head, or a repeat CT-head in patients unable to obtain an MRI, will be obtained at roughly T3 according to standard stroke imaging protocols. The total volume of infarcted tissue will be determined and recorded. Repeat

imaging usually between 24-72 hours is part of the standard of care for most stroke patients to ensure there has not been hemorrhagic conversion. Only these repeat imaging studies that were routinely obtained for standard patient care will be used for further determination of infarct progression. Specific study-dedicated imaging will not be obtained.

- c. The ratio of the volume of at-risk tissue (T0 – penumbral and infarcted tissue) to the volume of final infarct at subsequent reimaging will be compared between the placebo and hyperoxia groups. Volume assessments will be generated from both the CT-perfusion or non-contrast CT-Head at screening and the subsequent MRI using RAPID (iSchema View). These image files contain PHI, but are de-identified prior to processing by RAPID under the below process and PHI remains within the UCHealth firewall.

2. Analysis of serum markers of free radical ischemic-reperfusion injury and hyperoxic lung injury:

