17. DATA ANALYSIS PLAN

The primary endpoint of this study is feasibility. We hypothesize that the challenges of enrolling and randomizing AIS patients to a therapeutic intervention within less than one hour of ED presentation can be addressed. The number of potential subjects meeting the inclusion criteria and the relative rates of enrollment over time will be tracked. Additionally, the timing to enrollment and initiation of treatment intervention will be monitored. The primary endpoint of this study is feasibility as measured by the mean time from presentation to the ED to randomization and initiation of intervention. We hypothesize that we will be able to enroll, randomize and initiate treatment intervention in less than one hour for 80% of the enrolled subjects.

This study is not powered to detect significant differences in secondary or exploratory outcomes. However, analysis of secondary outcomes will occur both on an intention-to-treat and a per-protocol basis. Penumbral salvage will be reported as an average and as a standard deviation of the mean. We plan to enroll a total of 200 patients. Based on previous data that showed a decrease in the relative infarct volume growth (infarct volume at presentation/infarct volume at 4 hours) in patients treated with hyperoxia (87.8 +/-22%) compared to controls (149.1 +/- 41%)²⁹, 5 patients per arm would be needed to detect a similar difference with a power of 90% and type I error rate (α) of 0.05⁶². However, this effect was seen in a small study with less than 10 patients per treatment arm. Thus, such dramatic changes in infarct volume may not be expected, but even a smaller reduction in infarct volume will be clinically important as small reductions in infarct volume can have profound clinical effects if it is in a key cerebral territory. If you assume 20% of patients for some reason do not receive standard follow-up imaging to allow for calculation of infarct progression, a standard deviation of 41%, 80% power and α of 0.05, the proposed sample size will be able to detect an absolute difference in infarct volume growth of 18% between the control and hyperoxia.

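### The at-risk/final-infarct ratio is compared between arms without regard to baseline core and at-risk volume; a log-scale adjusted model would recover precision at almost no cost

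*Combined protocol and SAP*

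**What the plan says.** **Entry.** Section 4.1 gives two imaging routes. One is a RAPID mismatch, "a ratio of PWI_{Tmax>6} lesion volume/Infarct volume (with cerebral blood flow <30% normal) greater than 1.2". The other is an ASPECT score of 10 on non-contrast CT, which needs no perfusion volumes. Section 4.2, criterion 4 repeats the 1.2 threshold. Neither section writes a limit on core volume. Section 7, item 1(a) adds that the mismatch criteria rest on the standards of an outside trial, without spelling them out.

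**Outcome.** Section 7, item 1(c) takes the ratio of at-risk tissue at T0 (penumbra plus infarct) "to the volume of final infarct at subsequent reimaging will be compared between the placebo and hyperoxia groups". Section 17 says: "Penumbral salvage will be reported as an average and as a standard deviation of the mean". I take the item 1(c) ratio as the measure, since no other formula for salvage is given.

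**Analysis.** No model, transformation or covariate is named for this comparison. Section 6 describes randomization in blocks of 20, with no stratification by imaging. Section 7 says RAPID will calculate infarct and penumbral volume, and item 1(a) says total at-risk volume will be recorded.

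**Status.** Imaging is a secondary outcome meant to inform later trials (Section 4). Section 17 says the study is not powered for secondary outcomes, yet gives a detectable difference of 18% for infarct growth, using "a standard deviation of 41%, 80% power and α of 0.05".

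**The concern.** The ratio mixes two things: how much penumbra was saved, and how much there was to save. The second is known before randomization. With entry open to any mismatch above 1.2, subjects with the same proportional benefit can have very different scores, and high-mismatch subjects can dominate the average. An unadjusted comparison leaves that explainable spread in the error term. The raw ratio also becomes very large when the final infarct is close to zero, and is undefined at zero.

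At stake is the precision of the imaging estimate that the next trial is to be designed from. The validity of the randomized comparison is not in question.

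**Working it through.** **1. The plan's own figure.** Inputs: about 100 per arm (Section 4.1); 20% without follow-up imaging, SD 41, power 80%, α 0.05 (Section 17). Sidedness is not stated; two-sided reproduces the figure.

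- n = 100 × (1 − 0.20) = 80 per arm.
- Detectable difference = SD × √(2/n) × (z₀.₉₇₅ + z₀.₈₀) = 41 × √(2/80) × (1.960 + 0.842) = 18.2 (18.3 with the noncentral t). The stated 18% is reproduced.
- Power at 18 points is 79.3%.

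This calculation is for infarct volume growth, not for the item 1(c) ratio, so it carries over to the ratio only by assumption.

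**2. How the score depends on baseline.** Let C be core, A at-risk volume, M = A/C, and s the share of penumbra saved. If the final infarct is F = C + (1 − s)(A − C), the score is A/F = M / [1 + (1 − s)(M − 1)].

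- C = 100, A = 121, s = 0.5: 121/(100 + 10.5) = 1.10.
- C = 10, A = 50, s = 0.5: 50/(10 + 20) = 1.67.

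| M | none saved | half saved | all saved |
|---|---|---|---|
| 1.2 | 1.0 | 1.09 | 1.2 |
| 1.8 | 1.0 | 1.29 | 1.8 |
| 3 | 1.0 | 1.50 | 3 |
| 5 | 1.0 | 1.67 | 5 |
| 10 | 1.0 | 1.82 | 10 |

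**3. Rough value of adjustment alone.** Residual SD = 41 × √(1 − R²), 80 per arm. The documents give no R², so the range is an assumption.

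| R² | detectable difference | power at 18 points |
|---|---|---|
| 0 | 18.2 | 79.3% |
| 0.05 | 17.7 | 81.3% |
| 0.10 | 17.2 | 83.3% |
| 0.20 | 16.2 | 87.4% |
| 0.30 | 15.2 | 91.3% |
| 0.50 | 12.8 | 97.5% |

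With an assumed lognormal excess of M above 1.2 and a Beta-distributed share saved that is independent of M, log M explained about 6% to 32% of the score variance. That corresponds to roughly 82% to 92% power.

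**4. Raw ratio against the proposed model.** All inputs are assumed: core median 15 mL (log SD 1.0); M = 1.2 plus a lognormal excess with median 1.5; Beta-distributed share of penumbra lost; 80 per arm; 2,000 simulated trials per setting. The proposed model regresses log final infarct on treatment and both log baseline volumes.

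| mean share lost | log SD of excess | t-test on ratio | proposed model | gain (points) |
|---|---|---|---|---|
| 0.60 vs 0.48 | 0.7 | 76% | 89% | 13 |
| 0.60 vs 0.48 | 1.0 | 68% | 86% | 18 |
| 0.60 vs 0.48 | 1.3 | 60% | 82% | 22 |
| 0.50 vs 0.40 | 0.7 | 59% | 75% | 16 |
| 0.50 vs 0.40 | 1.0 | 48% | 71% | 23 |
| 0.50 vs 0.40 | 1.3 | 42% | 68% | 26 |

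Type I error of the proposed model was 4.0–5.2%. Sensitivity:

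- With 30% zero cores, in the second row's setting: 49% vs 82%.
- With 30% measurement noise on final volume, the gain falls to 6 points (41% vs 47%, type I error 6.1%; in a separate run, 37% vs 43%).

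**5. Where the gain comes from.** For the second row's setting, with Beta concentration 3: raw ratio 58%; raw ratio adjusted for both volumes 65%; log ratio unadjusted 69%; proposed model 78%. The log scale gives 69 − 58 = 11 points. Adjustment gives 65 − 58 = 7 points on the raw scale, or 78 − 69 = 9 on the log scale.

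The proposed model does not abandon the plan's measure. Since log(A/F) = log A − log F and log A is a covariate, the treatment coefficient is the same for log ratio and log final volume, with the sign reversed (apart from the 1 mL offset).

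**The case against.** - **The outcome is secondary and declared not powered.** This stands, and it limits the weight of the point. But Section 17 still gives an 80% power figure for imaging, and Section 4 wants the result to inform later trials, so precision has a use.
- **Randomization already protects the comparison.** This also stands. A reader might infer that chance imbalance in mismatch biases the result. It is ordinary sampling error, which a confidence interval covers; adjustment narrows that interval.
- **The plan is silent on the test.** Correct: it names no t-test. The simulations compare one natural reading of it with a better method.
- **Choice of score matters at least as much as covariates.** Largely right. In the simulations an unadjusted t-test on the fraction of penumbra saved did as well as or better than the proposed model (86% against 78% in the step 5 setting). However, the treatment effect was generated on that very fraction, without measurement error. The fraction divides by the penumbra, only 121 − 100 = 21 mL for the first example subject against 50 − 10 = 40 mL for the second, so errors in volume weigh most near the entry threshold.
- **ASPECTS-10 entrants may lack the covariates.** This stands. Item 1(a) speaks of recording at-risk volume after either scan, but does not say how a non-contrast CT would supply it. The share of such subjects is not given. If only half of the 80 per arm had perfusion volumes, 40 per arm would give a detectable difference of 25.7 and 50% power at 18 points (SD 41, unadjusted). Adjustment would not repair that.

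**Conclusion.** The point holds as a cheap gain in precision. The score depends on baseline mismatch by arithmetic, the written rule admits any ratio above 1.2, and no baseline adjustment is planned although RAPID calculates the volumes for subjects with perfusion imaging. The proposed model had higher power in every simulated setting. The gain was about 5 to 25 points without zero cores and more with many, but every input was assumed. The documents do not fix the size, and measurement noise shrinks it.

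Four stronger readings are not supported:

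- *The entry rule fixes how high a score can go.* It sets only the minimum baseline ratio. Even a subject's own ratio is a ceiling only if measured infarct never falls below measured core. Section 2 cites 120% penumbral salvage at 4 hours, and Section 17 cites relative growth of 87.8% and 149.1%; whichever way that ratio is read, one arm's later infarct averages below baseline.
- *Section 4 wrongly claims that the 1.2 rule selects small cores.* It says the imaging tools were used in earlier work to "identify patients who are early in their acute stroke trajectory with a small core infarct volume and remaining area suggestive of salvageable tissue"; it makes no such claim for this threshold.
- *The trial has no core limit.* None is written in Sections 4.1 or 4.2, but item 1(a) refers to outside standards that the documents do not reproduce.
- *The whole power gap is the price of not adjusting.* Much of it comes from the log scale.

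**What to change.** In Section 7, item 1(c) and Section 17:

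1. Make the between-arm imaging analysis a linear model of log(final infarct volume + 1 mL) on treatment, log(baseline core + 1 mL) and log(baseline at-risk volume + 1 mL), in subjects with baseline perfusion volumes. The 1 mL offset also handles zero volumes.
2. Report the adjusted ratio of final infarct volumes (hyperoxia to control) with a 95% CI. Keep the raw average and SD as a description.
3. Record baseline core volume explicitly, alongside total at-risk volume.
4. Report by arm how many ASPECTS-10 entrants lack perfusion volumes and so fall outside this analysis.
5. Reconcile the written 1.2 rule with the reference in Section 7, item 1(a) to an outside trial's mismatch standards. This asks for consistent text, not for a different eligibility rule.

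The cost is protocol and SAP wording and one regression. No new imaging is needed, because RAPID already calculates both volumes where perfusion imaging is done. There are two downsides: the result is a ratio of volumes, less familiar than a raw average, and it covers only subjects with perfusion volumes.
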